## 8.9 Post-ADRC Administration Follow-up visits: Weeks 2 ( $\pm 3$ days), 3 ( $\pm 3$ days) and 4 ( $\pm 3$ days)

The following assessments are to be conducted:

- Physical examination
- Vital signs
- Assessment for adverse events
- Concomitant medications
- Biomarkers

The following assessments, tests and questionnaires should be conducted in the order listed below (as applicable to each visit):

- Percent epithelialization of the graft
- Percent take of the graft
- Transepithelial water loss
- Digital photographs of wound with ruler to indicate the longest length and width
- Occurrence of complete wound closure

- Wound pain VAS
- Pruritis VAS at Weeks 3 and 4
- Patient and Observer Scar Assessment Scale (POSAs) (Weeks 3 and 4 only)

#### **8.10 Post-ADRC Administration Follow-up visits: Weeks 8 ( $\pm 7$ days), 12 ( $\pm 7$ days), 26 ( $\pm 14$ days), and 52 ( $\pm 21$ days)**

The following assessments are to be conducted:

- Physical examination
- Vital signs
- Assessment for adverse events
- Concomitant medications
- Biomarkers (Weeks 8 and 12 only)

The following assessments, tests and questionnaires should be conducted in the order listed below (as applicable to each visit):

- Digital photographs of wound with ruler to indicate the longest length and width
- Occurrence of complete wound closure (Weeks 8 and 12)
- Pruritis VAS
- Patient and Observer Scar Assessment Scale (POSAS)
- Vancouver Scar Scale (Weeks 12, 26 and 52 only)
- Skin elasticity (Delfin SkinElastimeter) measurement (Weeks 12, 26 and 52 only)
- Skin pigmentation (Delfin SkinColorCatch measurement) at Weeks 12, 26, and 52
- Skin hardness (Delfin SkinFibrometer measurement) at Weeks 12, 26, and 52

A summary table of all follow up evaluations is outlined in *Appendix A: Schedule of Procedures*.

#### **8.11 Early Termination Evaluation**

Subjects that discontinue early from the study, unless consent is withdrawn, shall have an Early Termination (ET) evaluation. This visit shall take place as soon as possible after it is determined that the Subject will be withdrawn from the study.

The observations and procedures for the ET evaluation are the same as those required at the Week 52 visit.

The reason for early withdrawal must always be clearly documented in the Subject's source documentation. Contact with the Subject must be attempted to determine overall health status, and contact details must be documented in the Subject's source documentation. If lost to follow-up, details of three contact attempts followed by a certified letter must be documented in the Subject source documentation.

## 9 RISK/BENEFIT ANALYSIS

### 9.1 Context of the proposed investigation:

Wound healing is a complex multifactorial process involving the interaction of inflammation, granulation tissue formation, re-epithelialization, and angiogenesis. For deep partial thickness and full thickness burns, acute burn management involves multiple activities including protecting the wound from further injury, initial cleansing and debridement and determination of dressings with or without a topical antimicrobial agent. Fluid resuscitation, prevention of hypothermia and pain management are also critical aspects of management. Surgical procedures involve escharectomy with further debridement and determination of skin grafting (often autologous split thickness skin graft (STSG) or a temporary graft (allograft or xenograft) or a tissue engineered substitute such as Integra®). The use of a tissue engineered substitute/matrix or temporary graft is generally followed by an autologous skin graft. Maturation of the graft may take several weeks and, depending on the severity and location of wound and the degree of meshing required for a STSG, the cosmetic outcome is often unsatisfactory. In addition, complications such as infection or contractures may occur, which can result in further treatments and procedures, as well as prolongation of healing. There is a need to develop improved techniques in acute burn management

Adipose Derived Regenerative Cells (ADRCs) are of emerging interest in the application of wound healing. Cells obtained from adipose tissue have been shown to inhibit inflammation, promote angiogenesis, stimulate recruitment of endogenous regenerative cells and promote salvage of damaged cells. On the basis of these properties, several preclinical studies have been performed using freshly isolated and cultured adipose-derived cells in a number of animal models of normal and impaired wound healing. The data consistently show improvement of epithelialization and wound healing. ADRCs are an advantageous resource because they can be found in abundant quantities, they can be harvested with a minimally invasive procedure, and they can be safely and effectively transplanted into an autologous host.

The Celution® System is designed to process lipoaspirated tissue to separate ADRCs from adipose tissue by enzymatic disassociation of the tissue and using buoyancy differences and centrifugation to separate and then concentrate the ADRCs from lipid containing adipocytes. When ADRCs are prepared using the Celution® System, the resultant cell suspension contains all of the components naturally occurring in the native tissue. Preparation of autologous ADRCs for delivery using the Celution® System involves no cell culture. The prepared ADRC dose can be administered to the same patient within four hours.

This study is a prospective, open-label, parallel group, usual care controlled, multi-center randomized (2:1, active: usual care alone) safety and feasibility study targeting thermal burns. Subjects will have at least one deep partial or full thickness burn wounds of  $\geq 250 \text{ cm}^2$  that is to be autografted with a split thickness skin graft (STSG). Subjects randomized to ADRCs will undergo small volume fat harvest (100 to 150 mL) performed at initiation of general anesthesia for scheduled burn surgery followed by intravenous delivery of ADRCs within 4 hours following completion of Celution processing. The lipoaspirate will be processed in the Celution® System to isolate and concentrate ADRCs.

Following informed consent and initial screening assessments, eligible subjects will undergo pre-operative testing. On the procedure day, subjects will be randomized to ADRCs (with usual care) or usual care alone. Low volume lipoharvest will only be performed on subjects randomized to ADRCs in order to obtain 100-150 mL lipoaspirate, which will then be transferred to the Celution® System for processing to

isolate and concentrate ADRCs for same-day administration. All treatment will be delivered in a total volume of 10 mL which will be delivered by slow intravenous administration.

Following surgery, subjects will be evaluated at several intervals up to 52 weeks to assess safety and efficacy as measured by direct measurement of wound healing.

## **9.2 Assessment of risks of the proposed Investigation**

The areas of risk include those of adipose tissue harvest and ADRCs delivery.

### **9.3 Risks**

The primary risks associated with adipose tissue harvest are bleeding and infection associated with the removal of the adipose tissue (fat harvesting procedure) along with the potential risk of infection associated with intravenous delivery of ADRCs.

Tissue harvest by syringe-based manual aspiration has been used as a source for ADRCs in the 344 subjects in 7 clinical trials with the Celution system. Adverse events were those commonly associated with liposuction such as discomfort and ecchymosis. The only related serious adverse event reported was a single event of rectus sheath hematoma which was associated with the use of a glycoprotein IIb/IIIa inhibitor. The patient had unremarkable recovery. Fat harvest has been demonstrated to be feasible and is associated with an acceptable safety profile. The volume of adipose tissue removed in these studies generally varied between 150 mL and 450 mL. In the proposed feasibility and safety trial in burn patients a target volume between 100 to 150 mL of adipose tissue is to be removed and processed for ADRCs.

## **9.4 Intravenous Delivery Risk Analysis and Management**

Risks involved with intravenous delivery of ADRCs cells include:

- Embolism
- Infection

The preclinical studies described herewith demonstrate no evidence of serious adverse events associated with ADRCs delivered intravenously, topically, subcutaneously, or intraarticularly. The clinical trial studies also have not reported significant safety issues when ADRCs are delivered subcutaneously, intraarticularly or intra-arterially. As in other trials applying intravascular administration of ADRCs, the ADRC product will be passed through a 47 $\mu$ m filter as part of the infusion process in order to further minimize risk of embolism. However, the possibility of infection exists with any percutaneous procedure. However, current experience in multiple clinical studies has not revealed any patient infections association with ADRCs delivery.

To mitigate potential risk of infection a gram stain of the ADRCs doses will be performed and must be negative in order to proceed with intravenous administration. A sample will be sent to the hospital laboratory for BacT (or equivalent) culture including aerobic microorganisms and sensitivity. All procedures related the Celution® System and cell counting are performed in aseptic conditions. If a culture result is positive for microbial activity, the investigator will be immediately notified. The study patient will be evaluated and standard clinical treatments of infection for patients with burn wound injury should be followed including antibiotics as deemed appropriate by the study investigator.

## **9.5 Celution® System and Delivery Device Risk Analysis and Management**

The investigators and all study personnel will be trained in the details of all aspects of the study procedures relevant to their particular area of responsibility.

- Train investigators and all study personnel in the details of the operation of the Celution System and Cytori Work Instructions for ancillary procedures and devices such as cell counting and intravenous delivery.
- Inspect the package integrity and sterility indicators on all disposables used with the devices and maintain sterility of the fluid paths.
- Follow Instructions for Use for the Celution® System, including all warnings, precautions and contraindications.

## **9.6 Fat Harvest Risk Analysis**

The risks of standard small volume liposuction in healthy patients are known and are minimal and recovery is usually fast. Following standard liposuction the following effects can be expected:

### Common

- Edema and redness of the liposuction areas for a few days
- Moderate contusion of the liposuction areas for a few months

### Uncommon

- Persistent edema
- Persistent bleeding
- Hematoma
- Visible puncture sites

### Rare

- Infection
- Deep Vein thrombosis (DVT)
- Persistent bleeding requiring transfusion

### **9.6.1 Fat Harvest Risk Management**

The Investigators and all study personnel will be trained in the details of all aspects of the study procedures. Standardization of fat harvest techniques is critical to a good clinical outcome. To minimize risks and increase the chances of a favorable clinical outcome the following measures are required for the liposuction procedure:

- Performed by an appropriately licensed and credentialed physician
- Monitoring of vital signs throughout the procedure
- Sterile technique is followed throughout
- The adipose tissue is handled gently at all times
- HGB, HCT prior to and 1-2 hours post-procedure

- To sufficiently induce local vasoconstriction/hemostasis during the fat harvest procedure, a minimum of 500 mL and a recommended maximum of 2000 mL of tumescent fluid is used containing:
  - 500 mL of Lactated Ringers solution
  - 20-50 mL of 1% Lidocaine
  - 1 mg of epinephrine
- A blunt 14 to 16 gauge LAMIS infiltrator (or equivalent) will be used for infiltration with tumescent solution
- After approximately 10 minutes, the adipose tissue may be harvested through the same incision, using the aspiration cannula attached to a syringe
- A blunt cannula with a minimum inner diameter of 3 mm is preferred for lipoaspiration.
- Lipoaspiration is done manually using a syringe (60 mL Toomey syringe is preferred); no machine aspiration is permitted.
- Monitoring for prevention or early detection of bleeding:
- Enrollment of only patients who qualify per the inclusion / exclusion criteria defined in the protocol) including screening blood work
- Strict adherence to the study protocol
- Standard of care for the monitoring and treatment of subjects who experience any adverse event for liposuction
- Target volume of adipose tissue is limited to approximately 100-150 mL
- Close surgical incision with appropriate suture
- Apply pressure bandage immediately upon conclusion of tissue harvest

Fat harvest should NOT be performed on patients who have received any anticoagulant within 1 hour of the procedure, substantial anticoagulation (eg: GIIb/IIIa inhibitor class drugs) within two weeks prior to fat harvest, or who have an abnormal PTT.

## 9.7 Overall Study Risk Management

The following measures implemented by Cytori will minimize the risks associated with patients' participation in clinical studies:

- All examinations, treatment procedures, and interpretation of clinical data generated during the study is directed, overseen and analyzed by an appropriately licensed and credentialed physician who has been trained to the clinical study protocol.
- Protocol and training programs to ensure that the study personnel at Cytori and at the clinical sites have a strong knowledge and understanding of the clinical protocol, including patient selection criteria and procedure requirements.
- Investigators are trained to the procedure requirements in the protocol, and the Instructions for Use for the Celution® System.
- Clearly defined inclusion and exclusion criteria to ensure that only properly selected patients will be enrolled in the clinical study.
- The protocol is designed so that patient treatment and follow-up procedures will be consistent with those of the clinically established standard of care.

## **9.8 Assessment of the Benefits of the Proposed Investigation**

This clinical investigation is designed as a safety and feasibility study. Therefore, it is not known at this time whether any direct subject benefit can be expected.

Patients with significant thermal burn injury typically require, on average, approximately 1 to 1.5 days of in-hospital care for each 1% of burned TBSA. Burn treatment involves labor-intensive procedures over a long period of time. For the patient, this includes substantial pain and morbidity from repeated excisions and harvest of skin autografts. Currently available preclinical data indicate that ADRC treatment may improve the quality of granulation tissue formed following escharectomy, promote more rapid re-epithelialization of the burn wound and reduce hypertrophic scar formation. These effects have the potential to improve the efficiency of integration of an autologous STSG into the wound site (commonly referred to as 'graft take'). They also have the potential to accelerate the rate at which the meshed component of the skin graft fills in with new epithelium. Earlier wound closure and improved graft take will likely lead to reduced risk of infection, shorter duration of stay, reduced rate of hypertrophic scarring formation and contracture, and reduced need for repeat procedures such as re-grafting and subsequent procedures to address hypertrophic scarring.

## **9.9 Consideration of Patient Preference information**

None can be provided at this time.

## **9.10 Assessment of Uncertainty**

The key source of the uncertainty in the available evidence is the safety of the procedure in burn wound subjects and the level of potential effect on wound healing and the improvement in the clinical course of the subject. The safety profile of liposuction in subjects with burn wounds has not been established. Liposuction, in order to obtain ADRCs via the Celution system, has been used in seriously ill subjects in several studies that evaluated the effects of ADRCs on congestive heart failure and in subjects with an acute myocardial infarction (MI) within a 72 hour window post MI. No adverse events occurred secondary to liposuction other than the one subject with a rectus sheath hematoma whose had received a glycoprotein IIb/IIIa inhibitor. The procedure of low volume liposuction appears to be tolerated in subjects with significant myocardial decomposition. The safety of the subjects in this trial will be evaluated within a staggered enrollment with safety evaluations as well as by a Data Monitoring Committee (DMC).

The extent of benefit to subjects is unknown as no other clinical trial using intravenously administered ADRCs in the treatment of burn wounds has been done. Preclinical data generated in animal models of burn wounds suggests that wound healing should be accelerated.

## **9.11 Conclusions**

The overall risk benefit profile with the proposed safety assessment measures makes the balance of risk to benefit sufficient to proceed with this clinical trial.

## 10 STATISTICAL METHODS AND DATA ANALYSIS

The RELIEF Trial is a multi-center, open-label, randomized, usual care controlled study to evaluate the feasibility and safety of ADRCs with usual care compared to usual care alone in subjects with thermal burns. The primary endpoint will be safety and feasibility.

The ITT population will be used for the primary analysis; the analysis will also be presented in the PTE population.

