#### **4.6 Study Endpoints**

##### ***4.6.1 Primary Endpoints***

- Safety and Feasibility

Safety will be evaluated based on the incidence, type and seriousness of adverse events related to the IV administration of test substance as well as the low volume lipoharvest procedure. Adverse events will be assessed according to the NIH Common Terminology Criteria for Adverse Events (CTCAE) v4.0 for scale grading adverse events.

Microbiological testing (culture and sensitivity) will be performed on the ADRC treatment dose produced and administered on site.

Feasibility will be determined as the ability to obtain  $> 100$  mL adipose tissue, obtain  $\geq 20 \times 10^6$  ADRCs, and deliver the prepared cell dose.

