### ***8.7.1.3 Fat Harvest Stopping Rules***

The physician performing the fat harvest procedure should continuously monitor the patient for signs of significant bleeding from the puncture site(s) and overall hemodynamic stability. The tissue harvest procedure should be terminated if any of the following occur:

- Drop in systolic blood pressure < 90 mm/Hg requiring pressor support
- Profuse or uncontrollable bleeding from the puncture site(s)
- Rapid expansion of subcutaneous space at the fat cell tissue harvest site(s) related to bleeding into the subcutaneous space
- Hemoperitoneum or pneumoperitoneum
- Hemothorax or pneumothorax
- Evidence of perforation of a vascular structure that requires ligature or surgical control
- Evidence of perforation into abdominal cavity, peritoneum or gastrointestinal organ

Should any of the above occur, the fat harvest procedure should be terminated and the patient treated according to standard of care. DO NOT PROCEED WITH ADRCs ADMINISTRATION. Complete the study specific SAE form and notify the sponsor within 24 hours.

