### ***8.7.3 ADRCs Delivery***

If subjects become hypotensive and require vasopressors to maintain organ perfusion between the collection of lipoaspirate and the intravenous introduction of ADRCs DO NOT PROCEED WITH ADRCs ADMINISTRATION.

Sterile technique should be maintained throughout the procedure. The intravenous ADRCs infusion will be administered by peripheral intravenous administration. An intravenous catheter (20 or 22 gauge) will be used to administer the ADRCs. The 5 mL output from the Celution System will be diluted to achieve 10 mL lactated Ringer's solution containing  $20 \times 10^6$  ADRCs in a sterile syringe. The syringe will be attached to the sterile macro (part # or designation) syringe filter and the contents of the syringe will be injected into the catheter slowly. The catheter will be flushed with 5 mL of lactated Ringer's solution from a separate sterile syringe.

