### 10.3 Data Analyses

Safety and efficacy endpoints will be summarized by treatment group using descriptive statistics (n, mean, SD, median, minimum and maximum), for quantitative variables and frequencies and percentages for categorical variables.

For quantitative efficacy variables, the change from baseline to each post-baseline time point will be analyzed using Student's t-test. For each endpoint, the treatment groups will be compared using two-sided tests at the alpha=0.05 level of significance.

The final dataset includes grafts with different mesh size (for example; 2:1 and 3:1). While the study is not powered for analysis of efficacy, data analysis for comparison between subjects receiving usual care and those receiving usual care plus ADRCs with respect to exploratory endpoints associated with healing (e.g.: percent epithelialization, pigmentation, hardness, Vancouver Scar Scale) will be stratified by mesh size (for example: 2:1, 3:1, 4:1, and all grouped).

Subjects randomized to the ADRC-treatment arm who undergo liposuction but who are not treated with ADRCs because the ADRCs do not meet release criteria may be followed up for the full duration of the study. Such subjects will be (a) included in the full data analysis for feasibility, (b) analyzed separately for safety, (c) analyzed in the ITT group for efficacy, and (d) excluded from the PTE group for efficacy.

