#### **10.5 Withdrawal, ITT, PTE**

Reasons for withdrawal pre- and post-randomization will be summarized. The treatment analyses will be performed on intent-to-treat basis as well as on a per-treatment-evaluable basis, as defined below:

Intent-to-Treat (ITT): All randomized subjects; randomization will occur on procedure day prior to the tissue harvest procedure. Subjects will be included in the analysis according to the treatment assigned if population is different than PTE.

Per-Treatment-Evaluable (PTE): All enrolled subjects who have day 5 follow-up information available.

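### The primary safety analysis is set in ITT, so ADRC-arm subjects uninfused for reasons other than a release failure stay in the denominator for infusion-related adverse events

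*Protocol*

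**What the plan says.** Protocol Section 10 gives safety and feasibility as the primary endpoint and continues: "The ITT population will be used for the primary analysis; the analysis will also be presented in the PTE population". Section 10.5 defines ITT as "All randomized subjects; randomization will occur on procedure day prior to the tissue harvest procedure", and PTE as "All enrolled subjects who have day 5 follow-up information available" (the Protocol Summary says day 6).

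Section 4.6.1 bases safety on "adverse events related to the IV administration of test substance as well as the low volume lipoharvest procedure". Section 10.3.1 summarizes adverse events by treatment group and analyzes related events in two parts: those tied to ADRCs and their delivery, and those tied to tissue harvest. It gives no denominator for either part and plans no confidence bound.

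Section 10.3 has one special rule. ADRC-arm subjects who "undergo liposuction but who are not treated with ADRCs because the ADRCs do not meet release criteria" are handled separately for safety, are in ITT for efficacy, and are left out of PTE for efficacy.

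Other sections describe further routes to no infusion. Section 8.7.1.1 bars harvest after a recent anticoagulant or with abnormally high INR or PTT. Section 8.7.1.3 lists reasons to terminate harvest and then instructs: "DO NOT PROCEED WITH ADRCs ADMINISTRATION". Section 8.7.3 withholds infusion "If subjects become hypotensive and require vasopressors to maintain organ perfusion between the collection of lipoaspirate and the intravenous introduction of ADRCs".

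**The concern.** An infusion-related event can be seen only in a subject whose infusion began, and a harvest-related event only in a subject whose harvest began. ITT is fixed before either procedure. An ADRC-arm subject who was never infused therefore adds one to the denominator of the infusion-related incidence and can never add to its numerator.

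The special rule in Section 10.3 shows that the plan recognizes the problem but solves it for one route only. It also departs from the unqualified statement in Section 10, so the two need reconciling.

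Section 9.10 says that no other clinical trial has given intravenous ADRCs for burn wounds, and Section 10.2 says these data will be used to design a larger study. With so few exposed subjects, what the safety result conveys depends heavily on how many were actually infused.

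**Working it through.** **Step 1. Which uninfused subjects remain in the ITT safety denominator?** Randomization takes place within 2 hours before surgery (Section 5.2), so each route below can arise after it.

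| Reason for no infusion | Section | Set apart for safety by Section 10.3? | Can be in PTE? |
|---|---|---|---|
| Cell count, viability or Gram stain fails release | 7.1.1, 7.2 | Yes | No (excluded for efficacy by 10.3) |
| Harvest not performed | 8.7.1.1 | No | No, if enrollment requires harvest to have begun (5.1) |
| Harvest terminated | 8.7.1.3 | No | Yes |
| Vasopressors needed before infusion | 8.7.3 | No | Yes |

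Three routes are left in the ITT denominator. Two of them can also be in PTE, because a harvested subject counts as enrolled (Section 5.1) and then needs only the follow-up information. In the other direction, an infused subject without that follow-up, or one given a prohibited medication (Section 8.4.1), is outside PTE. Neither planned set is the set of infused subjects.

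**Step 2. Arm size.** Up to 15 subjects at 2:1 gives 15 × 2/3 = 10 ADRC and 15 × 1/3 = 5 usual care. The protocol states no adverse event rate or precision target, so it has no figure of its own to reproduce here.

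**Step 3. Effect on the incidence.** Let x be the number of infusion-related events and k the number of ADRC-arm subjects uninfused by one of the three uncovered routes. The protocol gives no value for k, so 1 to 3 is assumed. No release failures are assumed; they would be handled separately.

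- ITT incidence = x / 10
- Incidence among infused subjects = x / (10 − k)
- Relative understatement = 1 − (10 − k)/10 = k/10

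| Events x | ITT (n=10) | k=1 (n=9) | k=2 (n=8) | k=3 (n=7) |
|---|---|---|---|---|
| 0 | 0% | 0% | 0% | 0% |
| 1 | 10.0% | 11.1% | 12.5% | 14.3% |
| 2 | 20.0% | 22.2% | 25.0% | 28.6% |

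The relative understatement is 10%, 20% or 30% for k = 1, 2 or 3 whenever at least one event occurs. With no events the percentage is the same, but it is reported as 0 of 10 when it rests on 9, 8 or 7 exposed subjects.

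**Step 4. Harvest-related events.** The same arithmetic applies, but only subjects whose harvest never started dilute this figure. A subject whose harvest was begun and then terminated was exposed and belongs in that denominator.

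**The case against.** The strongest reply has four parts.

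1. **Part of the problem is already handled.** A reader might infer from Section 10 that every never-infused subject dilutes the rate. That does not stand. Section 10.3 sets release failures apart for safety and assigns them to ITT for efficacy only, and the specific rule should govern the general sentence. For the same reason, the chance of a low cell yield is no measure of this problem.
2. **No bound is planned.** A reader might infer that a planned upper confidence bound is too favourable. Section 10.3.1 plans descriptive summaries only. Anyone computing a two-sided 95% exact bound for zero events would get 30.8% on 10 subjects and 36.9% on 8, but that is the reader's own calculation and not a result of the plan.
3. **The bias is conditional and its frequency unknown.** It needs at least one infusion-related event and at least one uninfused subject outside the Section 10.3 rule. Section 9.3 reports one related serious event of harvest in 344 subjects in earlier trials, which points to few terminated harvests. Section 9.10 adds that liposuction safety in burn patients is not established, and nothing is given for vasopressor need. No probability of non-infusion can be drawn from the document.
4. **The infused number should be visible, and denominators are SAP matter.** Delivery of the dose is a feasibility outcome, so a reader could redo the division.

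Points 1 to 3 stand and limit the finding. Point 4 stands in part. A reader could recover the figure, but the protocol does not leave the population open for the SAP to choose. It fixes ITT, and a SAP that follows it inherits the mismatch.

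**Conclusion.** The concern holds in a limited form. The population fixed for the primary safety analysis does not fit an endpoint defined by exposure, the special rule in Section 10.3 covers one route to non-infusion and leaves three, and PTE does not supply the missing set.

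If an infusion-related event occurs, its incidence is understated by a tenth for each uncovered uninfused subject: one event reads 10.0% instead of 11.1% to 14.3% for one to three such subjects. This rests on full enrollment at 15, an exact 2:1 split, and an assumed number of uninfused subjects. If none goes uninfused by those routes, there is no distortion. If there are no events, only the supporting number is overstated.

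The documents do not support saying that the rate will be too low, only that it can be. In an unpowered descriptive pilot the absolute effect is small, but the correction is worth making because it costs almost nothing.

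**What to change.** In Section 10.3.1, and in the SAP to match:

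- Summarize ADRC- and infusion-related adverse events over subjects in whom infusion was started.
- Summarize harvest-related adverse events over subjects in whom harvest was started, including those later not infused.

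In Section 10.3, extend the separate safety handling to every uninfused ADRC-arm subject, whatever the reason. Make clear that this does not remove harvested subjects from the harvest summary. In Section 10, qualify the ITT sentence so that it agrees: ITT remains the set for feasibility and for the between-arm comparison of all adverse events.

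The cost is a few sentences. No new data are needed, and sample size and conduct are unchanged. The one drawback for the sponsor is that the infusion-related incidence may become slightly less favourable, or a zero count may rest on fewer subjects.
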